3.3. Study Definitions and Derived Variables

3.3.1. Baseline Values

The baseline value will be defined as the last value obtained prior to the first vaccination/dose of study product. The Immunogenicity baseline for serum, mucosal secretion (vaginal, rectal and oropharyngeal) sample will be taken at enrollment day (Visit 01) and rectal mucosal biopsy baseline will be taken at visit 00C, which is 14 - 28 days before enrollment.

3.3.2. Immunogenicity Outcomes

In the primary, secondary, and exploratory outcomes, the GMT for Enzyme-Linked Immunosorbent Assay (ELISA) will be calculated for Days 1, 29, 43, 57 and 181 for each treatment arm. The GMT is defined as:

$$GMT = \sqrt[n]{X_1 * X_2 * X_3 * \dots * X_n}$$

In practice, it is the equivalent of: $GMT = \text{Exp}\{[\log(X_1) + \log(X_2) + \dots + \log(X_n)] / n\}$

Where the X_1, X_2, \dots, X_n are the titers for each participant at a certain timepoint. A sample SAS code for calculating the geometric mean and the 95% confidence interval is shown below.

```
proc surveymeans  
  data=data geomean;  
  var variable;  
  run;
```

The geometric mean fold rise (GMFR) for ELISA titers will be calculated for Days 29, 43, 57, and 181 compared to baseline titer in each study arm. The fold change for each participant at each timepoint is calculated first by dividing the follow-up titer by the baseline titer, then the geometric mean and 95% confidence interval will be calculated for each treatment arm at each timepoint.

Similarly, the ratio of serum to mucosal (rectal, vaginal, and oropharyngeal) IgG will be calculated at each time point. The geometric mean and confidence interval will be calculated as above.

Percent inhibition of gonococcal adhesion to human cervical cell line by mucosal antibody is defined as:

$$100\% * [(Titer \text{ without mucosal antibody} - Titer \text{ with mucosal antibody}) / Titer \text{ without mucosal antibody}]$$

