10 STATISTICAL CONSIDERATIONS

10.1 Study Hypotheses

The primary goal of this study is to assess the systemic and mucosal immunogenicity of two doses of 4CMenB compared to a placebo comparator. A secondary goal is to assess the safety and reactogenicity of 4CMenB. Though the study is not designed to formally test any hypotheses, p-values may be reported that compare the immunogenicity and/or safety data between treatment groups. The null hypotheses for these tests will be that there is no difference between treatment groups and the alternative hypotheses will be two-sided.

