10.2 Sample Size Considerations

A total of approximately 50 (maximum of 60), subjects will be enrolled and randomized to one of two study arms based on a 4:1 allocation ratio to the 4CMenB arm and placebo arm, respectively. The 4:1 allocation ratio was not selected based on any formal statistical criteria but instead was selected to maximize the number of subjects administered 4CMenB, and thus maximize the amount of immunogenicity data collected on subjects administered 4CMenB. Of the approximate 50 subjects, approximately 20 subjects will be enrolled into the Rectal Mucosal Biopsy Cohort. As with the overall sample size, this number was not selected based on any statistical criteria but was selected weighing the feasibility of enrolling subjects who would consent to the biopsy procedure against ensuring ample data was collected via rectal mucosal biopsy as there are no data on the impact of 4CMenB on immunologic responses at the human mucosal surfaces where GC is typically encountered.

The study is not designed to formally test any hypotheses associated with the immunogenicity data. Using the ELISA GMT estimates reported in [Table 2](#) of Semchenko et al.,¹³ estimated GMT 95% confidence intervals were calculated for the 4CMenB group using the post-vaccination estimates and for the placebo group using the pre-vaccination estimates. [Table 2](#) provides the estimated GMTs and GMT ratios between groups. To account for a small percentage of the approximate 50 randomized subjects not being eligible for the primary analysis (e.g., due to not having immunogenicity data available), a range of sample sizes from 36 to 50 was explored.

Table 2: 95% Confidence Intervals for GMTs and GMT Ratios across a range of Sample Sizes and Antigens

| N (Vaccine / Placebo) | Antigen ^a | Treatment Group | GMT Estimate | GMT 95% CI | GMT Ratio | GMT Ratio 95% CI |
|-----------------------------|----------------------|--------------------|-----------------|-----------------|--------------|---------------------|
| 30 / 6 | Ng OMV | Vaccine | 42224 | 35234, 50601 | 1.23 | 0.77, 1.97 |
| | | Placebo | 34297 | 16638, 70697 | | |
| | Ng whole cell | Vaccine | 78793 | 61639, 100721 | 1.62 | 0.86, 3.05 |
| | | Placebo | 48503 | 19329, 121713 | | |
| | Nm whole cell | Vaccine | 388023 | 262806, 572900 | 4.00 | 1.53, 10.47 |
| | | Placebo | 97006 | 29287, 321311 | | |
| | Ng rNHBA | Vaccine | 1176267 | 876783, 1578046 | 34.3 | 16.98, 69.26 |
| | | Placebo | 34297 | 16638, 70697 | | |

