10.3 Treatment Assignment Procedures

10.3.1 Randomization Procedures

Within each biopsy cohort (Rectal Mucosal Biopsy Cohort and No Rectal Mucosal Biopsy Cohort), subjects will be randomized 4:1 to 4CMenB or placebo. Randomization will be stratified by sex. Approximately twenty (20) subjects, approximately 10 males and 10 females, will be enrolled into the Rectal Mucosal Biopsy Cohort and approximately 30 subjects, approximately 15 males and 15 females, will be enrolled into the No Rectal Mucosal Biopsy Cohort.

The list of randomized treatment assignments will be included in the enrollment module of Emmes' Internet Data Entry System (IDES). Advantage eClinical® will assign each enrolled participant to a treatment arm after demographic and eligibility data have been entered into the system. A designated individual at each participating site will be provided with a coded list for emergency unblinding purposes, which will be kept in a secure place.

Instructions for use of the enrollment module are included in the Advantage eClinical User's Guide. Manual back-up procedures and instructions are provided for use in the event that a participating site temporarily loses access to the Internet or the online enrollment system is unavailable.

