6.4. Covariates and Subgroups

Randomization was stratified by sex; however, the protocol does not define any formal subgroup analyses, and the study is not adequately powered to perform subgroup analyses.

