8. IMMUNOGENICITY EVALUATION

This study was not designed to test a specific null hypothesis, rather, the objective was to characterize the immune response to GC elicited by the 4CMenB vaccine as compared with the placebo (normal saline) in healthy adult participants. Immunogenicity analysis will be presented for the Immunogenicity and PP populations. Immune responses for the study vaccine (4CMenB or placebo) will be summarized at each time point presented by study arm. Descriptive summary statistics will be provided for all assays and time points. For serum and mucosal antibody (IgG, IgA) assays by ELISA, the GMT and geometric mean fold rise (GMFR) will be calculated for each time point, (Days 1, 29, 43, 57, and 181 for GMT, and Days 29, 43, 57, and 181 for GMFR) in each study arm. Point estimates and their 95% confidence intervals will be reported for each time point. The distribution of titers will also be graphically summarized using reverse cumulative frequency distributions.

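### Day 1 IgG is collected from everyone, but the arms are summarised only by unadjusted GMT and simple fold rise; a supplementary baseline-adjusted arm ratio would be at least as precise at almost no cost

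*SAP*

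**What the plan says.** Protocol 3.1 has every subject give mucosal secretions, and SAP 3.3.1 places the serum and secretion baseline at Visit 01. Subjects are "randomized to one of two study arms based on a 4:1 allocation ratio to the 4CMenB arm and placebo arm, respectively" (protocol 10.2). Protocol 10.3.1 does this within each biopsy cohort and adds: "Randomization will be stratified by sex".

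The primary and secondary immunogenicity objectives compare 4CMenB with placebo. SAP 8, 8.1 and 8.2, with table shells 14 and 16, report for each arm and day an unadjusted GMT and, after Day 1, a GMFR: "Point estimates and their 95% confidence intervals will be reported for each time point". Day 1 enters only through the fold rise (SAP 3.3.2): "The fold change for each participant at each timepoint is calculated first by dividing the follow-up titer by the baseline titer".

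SAP 6.4, headed for covariates and subgroups, names no covariate: "Randomization was stratified by sex; however, the protocol does not define any formal subgroup analyses". Protocol 10.5.3 leaves supplementary and sensitivity analyses of these outcomes to the SAP, but SAP section 10 is marked not applicable. Protocol 10.1 leaves room for testing: "p-values may be reported that compare the immunogenicity and/or safety data between treatment groups". Neither document says which estimate such a p-value would rest on.

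**The concern.** With about 10 placebo participants, two things matter for any reading of one arm against the other.

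- **Precision.** A raw follow-up GMT ignores the baseline. A fold rise uses it but fixes its slope at 1 on the log scale, which adds noise when the correlation between Day 1 and follow-up is low. Which of the two is tighter depends on a correlation the documents do not give. A model that estimates the slope removes the need to guess.
- **Chance imbalance at Day 1.** The two planned summaries respond to it in opposite directions. If the vaccine arm happens to start higher, its GMT contrast is pushed up and its GMFR contrast is pushed down. The plan does not say how to read the two when they disagree.

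**Working it through.** **Inputs.** Protocol Table 2, Ng OMV at 40/10: vaccine GMT 42224 (36161, 49303), placebo GMT 34297 (20947, 56156), ratio 1.23 (0.85, 1.79). These are serum values from a cited study; the placebo row uses pre-vaccination data. The correlation rho between log Day 1 and log follow-up titer is not given, so I assume 0.3 to 0.8.

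**Reproducing Table 2.** SD(ln) = sqrt(n) × ln(upper/lower) / (2t).

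- Vaccine: sqrt(40) × ln(49303/36161) / (2 × 2.023) = 0.485.
- Placebo (pre-vaccination): sqrt(10) × ln(56156/20947) / (2 × 2.262) = 0.689.
- Pooled: sqrt[(39 × 0.485² + 9 × 0.689²)/48] = 0.529.
- SE of the log ratio: 0.529 × sqrt(1/40 + 1/10) = 0.187.
- ln(42224/34297) = 0.208; exp(0.208 ± 2.011 × 0.187) = 0.85 to 1.79, as stated.

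The same pooled-variance t interval reproduces all 12 ratio intervals in Table 2. A Welch interval does not (0.74-2.04 for Ng OMV at 40/10), so the figures below inherit Table 2's pooling.

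**Relative variance of the between-arm contrast**, with equal pre/post SD and the same slope in both arms: GMT 1; fold rise 2(1-rho); baseline-adjusted 1-rho². A 20,000-run simulation at rho 0.3, 0.5 and 0.7 gave SEs of 0.187, 0.188 and 0.187 for GMT; 0.220, 0.187 and 0.144 for fold rise; and 0.180, 0.165 and 0.134 for the adjusted estimate. Applied to the Ng OMV ratio at 40/10:

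| Assumed rho | GMT ratio CI | Fold-rise ratio CI | Adjusted ratio CI | Variance saved vs GMT | vs fold rise |
|---|---|---|---|---|---|
| 0.3 | 0.85-1.79 | 0.79-1.92 | 0.86-1.76 | 9% | 35% |
| 0.5 | 0.85-1.79 | 0.85-1.79 | 0.89-1.71 | 25% | 25% |
| 0.7 | 0.85-1.79 | 0.92-1.65 | 0.94-1.61 | 49% | 15% |
| 0.8 | 0.85-1.79 | 0.97-1.56 | 0.98-1.54 | 64% | 10% |

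Against the better of the two planned summaries, the saving peaks at 25%, at rho 0.5. That ceiling relies on equal SDs, and Table 2's own pre and post SDs (0.689 and 0.485) differ, so it is approximate. The adjusted column charges one degree of freedom, for baseline; adding sex moves the limits by about 0.01.

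**Per-arm intervals.** An adjusted arm mean has relative variance 1 - rho² × (other arm's share of N). At rho 0.5 this is 1 - 0.25 × 0.2 = 0.95 for vaccine and 1 - 0.25 × 0.8 = 0.80 for placebo, savings of 5% and 20%.

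**Day 1 imbalance.** One SE at 40/10 is 0.187 (pooled SD) or 0.689 × sqrt(1/40 + 1/10) = 0.244 (pre-vaccination SD), that is 1.21- or 1.28-fold. An imbalance of at least 1.23-fold in either direction has probability 27% or 39%. On the log scale, rho times the imbalance reaches the GMT contrast and -(1-rho) times it reaches the GMFR contrast. With 0.244:

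| Assumed rho | Shift in GMT contrast | Opposite shift in GMFR contrast |
|---|---|---|
| 0.3 | 1.08-fold | 1.19-fold |
| 0.5 | 1.13-fold | 1.13-fold |
| 0.7 | 1.19-fold | 1.08-fold |

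With 0.187 the smallest shift is exp(0.3 × 0.187) = 1.06-fold.

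**The case against.** The strongest reply is that the trial is descriptive: "The study is not designed to formally test any hypotheses associated with the immunogenicity data". The SAP plans no formal test of the primary outcome, and per-arm GMT and GMFR are what protocol 10.5.3 specifies. All of that stands, so this is not an error of execution. It does not remove the case for adjustment, because the objective is comparative and protocol Table 2 justifies the size of the trial by the width of a between-arm ratio interval.

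Several stronger readings are tempting, and the documents do not support them.

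- **That the plan leaves in a baseline imbalance as large as a planned effect.** A raw Day 1 imbalance of about 1.2- to 1.3-fold is indeed a 1-SE event. Only part of it reaches either summary, the fold rise does use the baseline, and shell 14 prints Day 1 GMTs by arm, so imbalance would be visible. The 1.23 is a serum ratio used to show interval width, not an effect the trial was planned around.
- **That adjustment would move an interval clear of 1.** A reader could find this in Table 2's Ng whole cell row, where 0.98-2.68 would become 1.05-2.51 at rho 0.5. The SAP's ELISA shells use OMV and NHBA antigens, not whole cells. The Ng OMV interval still includes 1 at rho 0.8.
- **That the intervals the SAP now reports would lose 25% of their variance.** That figure belongs to the between-arm ratio, which the SAP does not tabulate. The per-arm savings are the smaller ones worked out above.
- **That sex is ignored.** Stratification already limits imbalance by sex, and Tables 15 and 17 show results by sex. Those tables describe subgroups (about 5 placebo participants per sex) and do not adjust, but sex contributes little here; baseline drives the gain.

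**Conclusion.** The point holds as a nearly free improvement, not as a mistake in the plan. For the between-arm contrast, a baseline-adjusted estimate is at least as precise as either planned summary for rho between 0 and 1, apart from about 3 degrees of freedom. It also gives one estimate to read when GMT and GMFR are pulled apart by chance imbalance.

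The size is modest and conditional. It rests on an assumed rho, on serum inputs from a cited study, and on equal pre/post SDs with a common slope in both arms. The documents give no SD or correlation for rectal IgG, so the gain on the primary outcome cannot be stated.

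**What to change.** In SAP 6.4, name Day 1 log10 titer, sex and biopsy cohort as covariates. In SAP 8.1 and 8.2, add for each of Days 29, 43, 57 and 181 a supplementary linear model of log10 titer on arm and those three covariates. Report the adjusted arm ratio and adjusted GMTs with 95% CIs beside the planned GMT and GMFR, as added rows in Tables 14 and 16; nothing planned is removed. State that any between-arm immunogenicity p-value reported under protocol 10.1 comes from this model, two-sided as that section already requires.

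The cost is SAP wording, a few lines of SAS and about 3 degrees of freedom (48 to 45 at 40/10), using data already to be collected. Participants without a Day 1 result drop out of the adjusted rows, as they already do from the GMFR.

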4. INVESTIGATIONAL PLAN

4.1. Overall Study Design and Plan

This is a single site, phase 2, double blinded, mechanistic clinical trial to assess the systemic and mucosal immunogenicity of the multicomponent meningococcal serogroup B vaccine (4CMenB or Bexsero) against *N. gonorrhoeae* (GC), using a placebo vaccine (normal saline) as a comparator. Approximately 50 participants (maximum of 60 participants) who meet all eligibility criteria will be randomized 4:1 to one of two treatment groups. Group 1 (approximately N=40) will receive two doses of 4CMenB on Day 1 and Day 29. Group 2 (approximately N=10) will receive two placebo injections on Day 1 and Day 29. Both treatment groups include a rectal mucosal biopsy cohort and a no rectal biopsy cohort, and the participants in each cohort will be stratified by sex. The goal will be to ensure adequate representation of participants by sex in both groups (see [Table 1](#)).

Potential participants will be screened for eligibility during the screening visit(s). Informed consent will be obtained. All participants undergo a brief medical history and sexual history, a concomitant medication review, a directed physical examination, STI screening, etc. See the protocol for detailed eligibility criteria.

The screening/enrollment period will be approximately 6 months and participants will be followed through 6 months after their first vaccination. The duration of each participant's participation is approximately 8 months, from recruitment through the last study visit.

This clinical study will utilize a Safety Monitoring committee (SMC), which is an independent group of experts that advises the DMID. The primary responsibility of the SMC is to monitor participant safety.

4.2. Discussion of Study Design, Including the Choice of Control Groups

This study follows a double-blind, randomized, placebo concurrent control design. Participants receive either the multicomponent meningococcal serogroup B vaccine (4CMenB or Bexsero) against GC or saline placebo as their first study vaccination. After approximately 1 month, all participants will receive the second dose of study vaccine (or placebo). To date, there are no vaccines that are licensed in preventing gonorrhea, thus a placebo will be used as the comparator, which allows us to determine if the observed effects are due to the study product or other reason.

4.3. Selection of Study Population

The study population will include approximately 50 males and non-pregnant females, 18 to 49 years of age, inclusive, who are in good health and meet all eligibility criteria. Participants will be recruited from the community at large and enrolled at 1 VTEU site (Hope Clinic, Emory VTEU). This age range was selected to represent the population with the highest incidence of gonorrhea therefore children are excluded from this study. There are no plans currently to include children in future studies of mucosal immune responses to GC after meningococcal immunization.

4.4. Treatments

4.4.1. Treatments Administered

The multicomponent meningococcal serogroup B vaccine (4CMenB or Bexsero) against GC or saline placebo as study vaccination at day 1 and 29.

4.4.2. Identity of Investigational Product(s)

Bexsero or 4CMenB: Active Product. Each 0.5-mL dose of Bexsero (4CMenB) is formulated to contain 50 micrograms each of recombinant proteins NadA, NHBA, and fHbp, 25 micrograms of OMV, 1.5 mg aluminum hydroxide (0.519 mg of Al³⁺), 3.125 mg sodium chloride, 0.776 mg histidine, and 10 mg sucrose at pH 6.4 – 6.7. The NadA component is a fragment of the full-length protein derived from *N. meningitidis* strain 2996 (peptide 8 variant 2/3). The NHBA component is a recombinant fusion protein comprised of NHBA (peptide 2) and accessory protein 953 derived from *N. meningitidis* strains NZ98/254 and 2996, respectively. The fHbp component is a recombinant fusion protein comprised of fHbp (variant 1.1) and the accessory protein 936 derived from *N. meningitidis* strains MC58 and 2996, respectively. These 3 recombinant proteins are individually produced in *Escherichia coli* and purified through a series of column chromatography steps. The OMV antigenic component is produced by fermentation of *N. meningitidis* strain NZ98/254 (expressing outer membrane protein PorA serosubtype P1.4), followed by inactivation of the bacteria by deoxycholate, which also mediates vesicle formation. The antigens are adsorbed onto aluminum hydroxide. Each dose contains less than 0.01 micrograms kanamycin (by calculation).

Placebo: The placebo is 0.9% Sodium Chloride, USP injection.

4.4.3. Method of Assigning Participants to Treatment Groups (Randomization)

Enrollment/randomization will be performed through the enrollment module in the electronic data capture system, maintained by the Statistical and Data Coordinating Center (SDCC).

This study will enroll both male and non-pregnant female participants. The goal will be to ensure approximately adequate representation of participants by sex in both Treatment groups (**Table 1**). To facilitate this, randomization will be stratified by sex. Within each biopsy cohort (Rectal Mucosal Biopsy Cohort and No Rectal Mucosal Biopsy Cohort), participants will be randomized 4:1 to 4CMenB or placebo.

Approximately twenty (20) participants, 10 males and 10 females, will be enrolled into the Rectal Mucosal Biopsy Cohort and approximately 30 participants, 15 males and 15 females, will be enrolled into the No Rectal Mucosal Biopsy Cohort.

The list of randomized treatment assignments will be included in the enrollment module of Emmes' Internet Data Entry System (IDES). Advantage eClinical® will assign each enrolled participant to a treatment arm after demographic and eligibility data have been entered into the system. A designated individual at the site will be provided with a coded list for emergency unblinding purposes, which will be kept in a secure place.

Participant Inclusion and Exclusion Criteria (Section 5.1 of the protocol) must be confirmed by a study clinician licensed to make medical diagnoses and listed on the Form FDA 1572 as the site principal investigator (PI) or sub-investigator. No exemptions are granted on Participant Inclusion/Exclusion Criteria in DMID sponsored studies. Questions about eligibility will be directed toward the DMID Medical Officer.

4.4.4. Selection and Timing of Dose for Each Participant

Bexsero (4CMenB) or placebo will be administered as a 2-dose series (0.5-mL each) in participants randomized to each treatment arm. Both treatment arms will be enrolled and receive the first dose at day 1 (Visit 01) and will receive second dose at day 29 (Visit 04).

4.4.5. Blinding

This is a double-blinded clinical trial. Participants, site investigators, and study personnel who perform study assessments following study product administration, data entry personnel at the sites, and laboratory personnel performing study assays will be blinded to treatment assignment. Syringes will be labeled with an

overlay/blinding tape containing the participant ID, and the treatment number from the treatment key, and expiration time for the syringe, and provided to the unblinded vaccine administrator. The unblinded vaccine administrator will be credentialed to administer vaccines but will not be involved in study-related assessments, participant contact, or data collection following vaccination.

The SMC may receive data in aggregate and presented by study arm. The SMC may be unblinded to individual study treatment assignments, as needed, to adequately assess safety issues. The SMC will review grouped and unblinded data in the closed session only.

4.4.6. Prior and Concomitant Therapy

Concomitant medications will include all current medications and non-study vaccinations taken within 30 days before signing the ICF through approximately 28 days after the last study vaccination, and for new-onset chronic medical conditions through the final study visit for each participant. Participants who do not receive all vaccinations will have concomitant medications collected through approximately 28 days after the last vaccination, or early termination, whichever occurs first. Prescription and over-the-counter drugs will be included as well as herbals, vitamins, and supplements. See Section 7.1.2 of the study protocol for more detail.

